- The change from baseline in HbA1c will be analyzed using an ANCOVA model with treatment and the stratification factors as fixed effects and baseline HbA1c value as a covariate. The treatment differences in the least-squares means and the 2-sided 95% CI will be estimated based on this model. The last observation carried forward (LOCF) method will be applied when the Week 26 values are missing.

The following supplementary analysis will be performed using the primary estimand:

• A re-randomization test (Proschan 2011) (utilizing the MMRM as described above) will be used to determine the p-value for the primary efficacy comparison (ie, comparing all subjects who are randomized to canagliflozin to all subjects who are randomized to placebo). The re-randomization test will fix the observed HbA1c data, regenerate treatment assignments for the entire study using the same minimization algorithm employed in the study and compute the test statistics corresponding to the primary efficacy comparison. This process will be repeated at least 1,000 times. The p-value for the primary efficacy comparison will be defined as the proportion of re-randomized studies whose test statistic for that comparison is at least as extreme as that of the original treatment assignment.

[figure not shown]
The primary efficacy endpoint will also be performed in the subset of FAS subjects on a background of metformin (with or without insulin) using the main analysis methods described above. Analyses for the other AHA subgroups in the FAS may also be performed.

Additional details on the data handling rules (including the definition of data windows used for analysis) will be described in the SAP.

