5.1. Analysis Specifications

5.1.1. Level of Significance

Unless otherwise specified, all statistical tests will be interpreted at a 2-sided significance level of 5% and all confidence intervals at a 2-sided confidence level of 95%.

To strongly control the family-wise error rate at the 5% significance level, a sequential testing procedure as illustrated in Figure 1 below will be applied. The primary endpoint will be first tested in all subjects (i.e., FAS), and if the results are significant (2-sided alpha level of 0.05), it will then proceed to test the subset of subjects on a background of metformin (with or without insulin).

Figure 1: Testing Sequence

As the secondary efficacy endpoints listed in Section 5.3 are supportive in nature, no corresponding hypothesis testing will be performed and therefore they are not included in the testing sequence above.

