5.2.3. Analysis Methods

Primary Analysis

The primary analysis is based on the FAS dataset, including all HbA1c measurements collected from randomization to Week 26, including the measurements collected after treatment discontinuation or initiation of rescue medication.

The primary analysis will be based on pattern mixture model (PMM), as described below:

- Any intermediate missing data will be multiply imputed using Monte Carlo Markov Chains (MCMC), under a Missing at Random (MAR) assumption.
- Then the participants with ICEs and missing Week 26 HbA1c values will be multiply imputed using a multiple imputation (MI) model based on the participants with ICEs and non-missing Week 26 HbA1c values. An MI regression will be applied to impute all monotone missing values, using treatment group, stratification factors, baseline HbA1c and the change from baseline in HbA1c at Weeks 6, 12 and 20. If this MI model does not converge then a Copy Reference MI model will be used instead, as described in the sensitivity analysis section.
- Any Week 26 missing values for change from baseline in HbA_{1c} in participants without ICEs will be imputed based on the MI regression (see description above) applied to all participants.
- A total of 1000 multiple imputations will be performed. A seed equal to 345 will be used in all MI models.
- After MI, each of the multiply imputed datasets will be analyzed using analysis of covariance (ANCOVA) with terms for treatment, stratification factors, and baseline HbA_{1c}.
- Rubin's rules will be applied to combine the ANCOVA results across the imputed datasets, including the Week 26 LS Means for each treatment group and the difference vs placebo in LS Means.

Secondary analysis of the primary efficacy endpoint

The secondary analysis is based on a subset of subjects on background metformin (with or without insulin) from the FAS dataset, including all HbA1c measurements collected from randomization to Week 26, including the measurements collected after treatment discontinuation or initiation of

rescue medication. The attributes of estimand for this analysis is the same as the primary efficacy estimand except the population is a subset of subjects with background metformin (with or without insulin). The same analysis based on PMM will be performed as described above.

Bayesian analysis of the primary efficacy endpoint

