- The primary efficacy endpoint will be analyzed using a mixed model for repeated measures (MMRM) based on restricted maximum likelihood. The analysis will use the observed data and will include the fixed, categorical effects of treatment, stratification factors (ie, background AHA and age group), visit, and treatment-by-visit interaction, as well as the fixed,

continuous covariates of baseline and baseline-by-visit interaction. An unstructured covariance will be used to model the within-patient errors. In case the model does not converge using the unstructured covariance then alternative covariance structures (such as compound symmetry and AR(1)) will be considered.

• The change from baseline in HbA_{1c} will be analyzed using an ANCOVA model with treatment and the stratification factors as fixed effects and baseline HbA_{1c} value as a covariate. The treatment differences in the least-squares means and the 2-sided 95% CI will be estimated based on this model. The last observation carried forward (LOCF) method will be applied when the Week 26 values are missing.

In addition, based on the FAS with the data collected up to Week 26, the following supportive analysis will be performed:

- A re-randomization test (Proschan 2011) (utilizing the MMRM) will be used to determine the p-value for the treatment comparison of the primary efficacy endpoint (ie, comparing all subjects who are randomized to canagliflozin to all subjects who are randomized to placebo). The re-randomization test will fix the observed HbA_{1c} data, regenerate treatment assignments for the entire study using the same minimization algorithm employed in the study and compute the test statistics corresponding to the treatment comparison. This process will be repeated at least 1,000 times. The p-value for the treatment comparison will be defined as the proportion of re-randomized studies whose test statistic for that comparison is at least as extreme as that of the original treatment assignment.
- A supportive analysis of the primary endpoint will be conducted based on the 26-week PP analysis set using the same mixed model with repeated measures as in the sensitivity analysis.

Subgroup Analyses

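### The supportive re-randomisation test takes its p-value as a raw proportion of as few as 1,000 draws, so it can report p = 0 and is imprecise when the exact p is close to 0.05

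*SAP*

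**What the plan says.** SAP 5.2.3 holds the observed HbA1c data fixed, regenerates the treatment assignments with the study's minimisation algorithm, and computes the test statistic from the MMRM each time. On the number of draws and the p-value: "This process will be repeated at least 1,000 times. The p-value for the treatment comparison will be defined as the proportion of re-randomized studies". The studies counted are those with a result no less extreme than under the original assignment. Protocol 11.3.1 and the protocol synopsis give the same definition: "The p-value for the primary efficacy comparison will be defined as the proportion of re-randomized studies whose test statistic for that comparison". The condition for being counted is the same there.

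Neither document counts the observed assignment among the draws, fixes B above the minimum, gives a seed for this test, or asks for an interval around the estimate. SAP 5.2.3 does fix 1,000 imputations for its primary and copy-reference analyses, with a seed: "A seed equal to 345 will be used in all MI models". That seed does not reach the re-randomisation test, which uses the MMRM and no imputation.

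On status, the SAP introduces the test with the words "the following supportive analysis will be performed", and the protocol calls it supplementary. SAP 5.1.1 states that "all statistical tests will be interpreted at a 2-sided significance level of 5" per cent, without saying whether a value of exactly 0.05 counts as significant.

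**The concern.** Subjects are allocated by minimisation. Of the analyses listed in SAP 5.2.3, this is the only one that refers the result to the allocation procedure actually used; the pattern mixture, copy-reference, tipping-point, MMRM and LOCF analyses all rest on a model. Such a check is most useful when the main result is close to 0.05, which is where 1,000 draws are least able to settle the matter.

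Two features of the rule cause difficulty. First, b/B is zero whenever no draw is as extreme as the observed statistic, although the observed assignment is itself a possible assignment and the exact p cannot be zero. Second, a floor of 1,000 draws with no seed means that the reported figure depends on the random stream and on when sampling stopped. At stake is whether the report can take this p-value at face value, not whether the trial succeeds.

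**Working it through.** **Inputs.** B of at least 1,000 and p-hat = b/B (SAP 5.2.3; protocol 11.3.1). Two-sided level 0.05 (SAP 5.1.1). Planning assumptions from SAP 1.4, used only to gauge how often the problem would arise: effects 0.5, 0.4 and 0.5 percentage points, SD 0.9, half of the subjects re-randomised 1:1 at Week 12, 66 per group. In what follows, the exact p is the value that B would approach without limit.

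**1. The plan's own figure.** The documents give no Monte Carlo error, so the figure to reproduce is the sample size. The mean effect is 0.5 × 0.5 + 0.25 × 0.4 + 0.25 × 0.5 = 0.475. Then n = 2 × (1.960 + 1.036)² × 0.9² / 0.475² = 64.5, so 65 per group against 66 stated. Power at 66 is 85.3% by the noncentral t. The planning inputs are consistent.

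**2. Monte Carlo error.** Given the exact p, b is Binomial(B, p). At p = 0.05 and B = 1,000 the standard error is √(0.05 × 0.95 / 1000) = 0.0069, and the 95% range is 0.05 ± 1.96 × 0.0069 = 0.0365 to 0.0635. At B = 10,000 the standard error is 0.0022 and the range 0.0457 to 0.0543.

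**3. Chance of the wrong side of 0.05**, from the binomial distribution, counting p-hat ≤ 0.05 as significant:

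| Exact p | B = 1,000 | B = 10,000 |
|---|---|---|
| 0.035 | 0.6% | about 0 |
| 0.040 | 4.9% | about 0 |
| 0.045 | 19.9% | 0.8% |
| 0.055 | 27.0% | 1.4% |
| 0.060 | 10.1% | about 0 |
| 0.065 | 2.8% | about 0 |

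With a strict rule, p-hat < 0.05, the figures at 0.045 and 0.055 are 24.2% and 22.5% at B = 1,000, and 0.9% and 1.2% at B = 10,000.

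**4. Average over the planned design.** The expected z is 0.475 / (0.9 × √(2/66)) = 3.03, which corresponds to p = 0.0024. Taking z as normal with mean 3.03 and SD 1, the exact p falls between 0.0365 and 0.0635 in about 5% of trials. The wrong-side chance at B = 1,000, averaged over all trials, is about 1%.

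**5. Chance of a reported zero.** P(b = 0) = (1 − p)^B. At B = 1,000 this is 0.999^1000 = 36.8% for an exact p of 0.001, and 8.8% for 0.0024. Averaged over the same distribution of z it is about 35%. The upper limit of the 95% Clopper–Pearson interval for zero out of 1,000 is 1 − 0.025^(1/1000) = 0.0037.

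**6. Size.** Under the null with a continuous statistic, b is uniform on 0 to 1,000. Rejecting when b/B ≤ 0.05 admits b = 0 to 50, so the size is 51/1001 = 5.09%. Rejecting when b/B < 0.05 admits b = 0 to 49, so the size is 50/1001 = 4.995%. With (b+1)/(B+1) the size is 50/1001 under either rule, and the smallest possible value is 1/1001.

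**7. What each change does.** The added one removes the zero and the dependence on the tie rule. It does not reduce Monte Carlo error: at B = 1,000 with the added one, the wrong-side chances at 0.045 and 0.055 are still 24% and 23%. Only a larger B lowers them.

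**The case against.** The strongest reply is that nothing in the plan turns on this p-value. The formal sequence in SAP 5.1.1 tests the primary endpoint in the full analysis set and then in the metformin subset. The primary analysis is the pattern mixture model with ANCOVA, and the Bayesian analysis is triggered by that analysis. This stands, and it makes the point minor.

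Second, b/B is a recognised, unbiased estimate of the exact p, and a zero can be printed as below 0.001. In part this stands: after a zero, the 0.0037 limit leaves the answer well below 0.05. But the SAP defines the p-value as the proportion itself and has no rule for printing a zero, and the limit of 0.0037 shows that below 0.001 would claim more than 1,000 draws support.

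Third, a reader might infer that the test is too liberal as written. The documents do not support that without a condition: the excess is 0.09 percentage points at B = 1,000, it appears only if a value equal to 0.05 counts as significant, and the SAP does not state that rule.

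Fourth, at least 1,000 is a floor, and the sponsor may already intend more draws. That is possible. A reader might go further and suspect that draws would be added after a first look. The plan does not exclude it, but nothing in the documents suggests it, and further draws move the estimate towards the exact p.

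Fifth, the 20% and 27% figures belong to chosen borderline values. That stands, which is why the average of about 1% belongs beside them.

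**Conclusion.** The concern holds as a minor point about a supportive analysis. As written, the rule can report p = 0, about 35% of the time under the planned design with 1,000 draws. It can also misplace the result relative to 0.05 through simulation error alone, but only when the exact p lies between about 0.037 and 0.064.

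It does not follow that the trial's confirmatory result or its type I error is at risk. The test lies outside the testing sequence, and the size excess is negligible or absent.

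The binomial results assume independent draws. The 35% and 1% averages rest on a normal approximation with an effect of 0.475, SD 0.9 and 66 per group; covariate adjustment and missing data in the actual MMRM would shift them. All figures for 1,000 draws describe the least that the SAP allows, not necessarily what will be run.

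**What to change.** In SAP 5.2.3, define the p-value as (b+1)/(B+1), where b is the number of regenerated studies at least as extreme as the observed one. Fix B at 10,000, state a seed for this test, and report the Monte Carlo 95% interval with the p-value. The protocol's minimum of 1,000 already permits 10,000 draws. With both changes, the wrong-side chances at an exact p of 0.045 and 0.055 become 0.9% and 1.2%, and the smallest reportable value is 1/10,001.

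The cost is a few lines of text, computing time for ten times the minimum number of MMRM fits, and more fits that may not converge. SAP 5.2.3 already provides for other covariance structures if the unstructured one fails, but names them only as examples and does not mention the regenerated datasets. Write the fallback down as an ordered rule, and apply it in the same way to the observed data and to every draw. These changes should be made before unblinding.

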5.3. Secondary Efficacy Endpoints

5.3.1. Definition

The secondary efficacy endpoints at Week 26 and Week 52 include:

- Change from baseline in FPG.
- The proportion of subjects with $HbA_{1c} < 7.5\%$, <7.0%, and <6.5%.
- Time to rescue and proportion of subjects receiving rescue therapy.

- Percent change from baseline in body weight.
- Change from baseline in BMI.
- Percent change from baseline Fasting plasma lipids (ie, LDL-C, HDL-C, total cholesterol, non-HDL-C, LDL-C to HDL-C ratio, non-HDL-C to LDL-C ratio, and triglycerides).
- Change from baseline in SBP and DBP.

The secondary efficacy endpoint at Week 12 and Week 52:

• Change from baseline in HbA_{1c}.

The analysis of the above endpoints will use the same attributes of the primary estimand except that the population level summary for the categorical endpoints will be difference in proportions.

5.3.2. Analysis Methods

The estimands for the secondary endpoints are the same as for the primary efficacy endpoint except for the variable.

Continuous endpoints (except for triglycerides) will be analyzed with an MMRM model as described before in the FAS population. For the endpoints with post-baseline assessments taken only at Week 26 and Week 52, an analysis of covariance (ANCOVA) model similar to the primary efficacy endpoint will be used at Week 26. The least-squares means for the treatment comparisons and their 2-sided 95% confidence intervals will be estimated based on this model. The analysis of percent change in triglycerides may be based on nonparametric methods (given the anticipated skewed nature of this parameter) or alternative methods.

The categorical secondary efficacy endpoint of maintaining HbA_{1c} <7.0% (and HbA_{1c} <6.5% and HbA_{1c} <7.5%) will be analyzed longitudinally using a generalized linear mixed model in the FAS population. The model will include the fixed, categorical effects of treatment, stratification factors (ie, background AHA and age group), visit, and treatment-by-visit interaction, as well as the fixed, continuous covariates of baseline and baseline-by-visit interaction. An unstructured covariance will be used to model the within-subject errors. The odds ratio and 2-sided 95% CI for the treatment comparisons at Week 26 (canagliflozin compared to placebo) will be estimated based on this model. It is possible that the generalized linear mixed model may fail to converge for the binary secondary efficacy endpoint of the proportion of subjects with HbA_{1c} <7.0% (and HbA_{1c} <6.5% and HbA_{1c} <7.5%) due to few subjects meeting the threshold. In this case, a logistic regression model will be used. The model will include treatment and stratification factor as fixed effects, and baseline HbA_{1c} value as a covariate. This alternative approach will be applied on the LOCF data at Week 26/Week 52 and the observed data by visit. Odds ratios and the 2-sided 95% CIs for the treatment comparisons will be derived from the model.

The time to event data (e.g., time to receiving rescue therapy or discontinuing due to need for rescue therapy) will be plotted using the KM method. The difference in proportion of subjects receiving rescue therapy or discontinuing due to need for rescue therapy between canagliflozin and placebo with 95% confidence intervals will be provided.

22

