1.4. Sample Size Justification

The primary hypothesis of the study is that canagliflozin is superior to placebo in glycemic control, as measured by the change from baseline to Week 26 in HbA_{1c}.

The sample size calculation is based on the 2-stage randomization design using a 2-sample, 2-sided t-test with Type 1 error rate of 0.05. Based on the following assumptions on treatment effect (0.4% to 0.5% change in HbA_{1c}) and an associated common standard deviation (SD) of 0.9% and assuming 50% of the subjects will meet the re-randomization criteria at Week 12, it is estimated that at least 66 subjects per group will be required to achieve approximately 85% power. To account for attrition due to study discontinuation in a longitudinal analysis (to be described below), a 10% sample size inflation factor is employed (Lu 2008), and a total of at least 146 subjects (73 per arm) will be randomized in this study.

Treatment group	Meeting re- randomization criteria at Week 12	Placebo-subtracted group difference in change in HbA _{1c} from baseline to Week 26
canagliflozin 100 mg to canagliflozin 100 mg	No	0.5%
canagliflozin 100 mg to canagliflozin 100 mg	Yes	0.4%
canagliflozin 100 mg to canagliflozin 300 mg	Yes	0.5%

For subjects who are on background metformin (with or without insulin), it is estimated that at least 33 subjects per group (after accounting for attrition due to study discontinuation) will be required to achieve approximately 85% power to assess the efficacy of canagliflozin on a background of metformin.

Treatment group (add-on to metformin)	Meeting re- randomization criteria at Week 12	Placebo-subtracted group difference in change in HbA _{1c} from baseline to Week 26
canagliflozin 100 mg to canagliflozin 100 mg	No	0.75%
canagliflozin 100 mg to canagliflozin 100 mg	Yes	0.65%
canagliflozin 100 mg to canagliflozin 300 mg	Yes	0.75%

The assumed treatment effect above is based on a subgroup analysis of subjects with baseline eGFR of \geq 90 mL/min/1.73m² from the add-on to metformin study of canagliflozin in adults (ie, Study DIA3006).

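### HbA1c change at Week 52 and the HbA1c targets carry the primary treatment-policy estimand but not its handling of values missing after discontinuation or rescue, so the Week 52 difference may be overstated

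*SAP*

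**What the plan says.** **Estimand.** SAP 5.2.2 applies a treatment-policy strategy to treatment discontinuation and rescue. SAP 5.3.1 carries this over to the secondary endpoints: "The analysis of the above endpoints will use the same attributes of the primary estimand", except that the summary for categorical endpoints is a difference in proportions. SAP 5.3.2 and Protocol 11.3.3 likewise carry over the primary estimand.

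**Primary endpoint (Week 26 change).** SAP 5.2.3 separates missing values by ICE status: "Then the participants with ICEs and missing Week 26 HbA1c values will be multiply imputed using a multiple imputation (MI) model", fitted to participants with ICEs who do have a Week 26 value. Copy Reference is the fallback for non-convergence. Copy Reference and a tipping-point analysis are also sensitivity analyses, as are MMRM and LOCF ANCOVA.

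**HbA1c change at Week 52.** A major secondary objective in SAP 1.1. SAP 5.3.2: "Continuous endpoints (except for triglycerides) will be analyzed with an MMRM model as described before in the FAS population". No other analysis is given.

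**HbA1c <7.5%, <7.0%, <6.5%.** SAP 5.3.1 lists these at Weeks 26 and 52. SAP 5.3.2 specifies a GLMM with an odds ratio at Week 26. If it fails to converge, logistic regression is applied to LOCF data at Weeks 26 and 52 and to observed data by visit.

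**Follow-up.** Protocol 10.2.4 keeps subjects who stop drug in the visit schedule where possible. Those who will not return may be contacted for adverse events and medications only, which yields no HbA1c.

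**The concern.** One estimand is paired with two treatments of the same gap. At Week 26, a subject who stopped drug and has no HbA1c is imputed from others with an ICE. At Week 52, the MMRM in SAP 5.2.3 has no term for ICE status, so that subject's value is implicitly predicted from everyone in the arm, most of whom may still be on drug. If the effect fades off drug, that prediction is too favourable to canagliflozin.

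The targets add a second inconsistency. At Week 26 the mean change and the proportion below 7.0% would rest on different implied values for the same missing subjects. The LOCF fallback can also carry forward a value measured on drug.

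At stake are the Week 52 estimate and interval, and the coherence of the Week 26 mean with the Week 26 targets.

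**Working it through.** **1. The plan's own figure.** Inputs from SAP 1.4:
- Test: "using a 2-sample, 2-sided t-test with Type 1 error rate of 0.05".
- Size: "at least 66 subjects per group will be required to achieve approximately 85% power".
- Spread, in HbA1c %: "an associated common standard deviation (SD) of 0.9".
- Effect: "assumptions on treatment effect (0.4% to 0.5% change in" HbA1c).
- Share re-randomized: "assuming 50% of the subjects will meet the re-randomization criteria at Week 12", then split 1:1.

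Mean effect = 0.50 × 0.5 + 0.25 × 0.4 + 0.25 × 0.5 = 0.475. The normal approximation, 2(1.960 + 1.036)² × 0.9² / 0.475², gives 65 per group. The noncentral t gives 66, with power 85.3%. 66 × 1.10 = 72.6, so 73 per arm. The plan's figures reproduce, and 0.475 is the reference effect below.

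**2. Simple dilution at Week 52.** Let a share m of the canagliflozin arm be missing after stopping drug, with the effect wholly lost. If no stopper is retrieved, a missing-at-random (MAR) model targets δ and the treatment-policy value is δ(1 − m). The overstatement is δm. With δ = 0.475:
- m = 5%: 0.451; overstated by 0.024
- m = 10%: 0.428; overstated by 0.048
- m = 20%: 0.380; overstated by 0.095

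For scale, the standard error at the planned size is 0.9 × √(2/66) = 0.157, so 0.095 is about 0.6 of a standard error. The values of m and the full loss of effect are assumptions. The documents' only attrition figure is the 10% inflation factor.

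**3. Partial retrieval.** Large-sample simulation with 400,000 per arm. Assumed: correlation 0.85 between adjacent visits, stopping spread evenly over visits, immediate full loss of effect, no rescue.
- 10% stop, half missing: truth −0.428, MAR −0.450 (0.022 overstated), ICE-based imputation −0.427
- 20% stop, half missing: truth −0.381, MAR −0.424 (0.043), ICE-based −0.380
- 20% stop, none missing: all −0.381

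**4. With rescue.** Same set-up, with rescue in 10% of canagliflozin and 30% of placebo subjects (those with the highest Week 26 values) and an assumed rescue effect of −0.8.
- 10% stop; half missing after any ICE: truth −0.268, MAR −0.335, ICE-based −0.269
- 10% stop; half missing after stopping, none after rescue: truth −0.268, MAR −0.291, ICE-based −0.280
- 20% stop; 80% missing after stopping, 20% after rescue: truth −0.221, MAR −0.308, ICE-based −0.256

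In the last two cases the ICE-based step leaves an error of 0.012 out of 0.023, and 0.035 out of 0.087. The reason is that rescued subjects continue study drug (Protocol 6.2.2), so as donors they lend a drug effect to subjects who stopped. Another run with rescued subjects as donors gave truth −0.286, MAR −0.321 and pattern-mixture −0.316, removing only 0.005 of 0.035. The gain depends on who the donors are.

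**5. Targets at Week 26.** A separate simulation assumed effect loss within 12 weeks off drug, 20% to 30% off drug by Week 52 and 60% to 80% of those missing. The target difference was 11.1 points in truth, 11.6 to 11.9 under MAR and 11.4 under pattern-mixture. The shift is small (at most 11.9 − 11.1 = 0.8 points). The clearer faults are in the text: the models yield odds ratios where SAP 5.3.1 names a difference in proportions, and a Week 52 contrast appears only in the fallback.

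**The case against.** **MMRM is not contrary to the estimand.** Treatment policy means using values observed after an ICE, and nothing in SAP 5.3.2 excludes them. How to fill what remains missing is a modelling assumption. SAP 5.2.3 declares all its sensitivity analyses, MMRM included, aligned with the primary estimand. The primary analysis itself uses MAR for intermediate gaps and an all-participant regression for missing Week 26 values without an ICE. Protocol 11.3.1 still makes MMRM primary for one health authority, although SAP Amendment 3 dropped that sentence. This stands, so a reader who infers that the Week 52 analysis violates its estimand goes too far. What remains is that the SAP uses a closer match at Week 26 and gives no reason for dropping it at Week 52.

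**Missing data may be few.** Stoppers are followed where possible, Weeks 26 and 52 are key visits on the reduced schedule, restarting drug is to be considered at every visit, and rescue does not end data collection. This stands, and it is why no definite bias can be claimed.

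**The donor pool may be thin.** With 20% off drug and 60% of those missing, 73 × 0.20 × 0.40 = 5.8 retrieved stoppers per arm remain. With 30% and 80%, 73 × 0.30 × 0.20 = 4.4. Rescued subjects add to these, and the regression pools both arms, but it has about 13 coefficients (intercept, treatment, three for AHA background, age, baseline, six earlier visits). This stands as a limit on the fix. It is a reason to pre-specify Copy Reference and tipping-point analyses.

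**Conclusion.** The mismatch is in the text. HbA1c change at Week 52 and the targets share the primary estimand, but have neither its ICE-based imputation nor a missing-not-at-random sensitivity analysis. The Week 52 difference may be overstated by about 0.02 to 0.10 HbA1c points, assuming 5% to 20% missing after stopping and full loss of effect. With complete follow-up the overstatement is zero.

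Three stronger readings are tempting and not supported:
- That late benefit is overstated. The documents give no Week 52 missing rate and no outcomes after ICEs, on which size and direction depend.
- That the targets are a late result under MAR, using a method demoted to sensitivity. The GLMM contrast is at Week 26, the only Week 52 target analysis is the fallback on LOCF and observed data, and the GLMM is not among the primary endpoint's sensitivity analyses.
- That a confirmatory claim or the error rate is affected. SAP 5.1.1 treats these endpoints as supportive and untested, so only estimates and intervals are concerned.

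The point is worth correcting, but does not threaten the primary analysis.

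**What to change.** 1. Analyse HbA1c change at Week 52 with the primary pattern-mixture imputation, adding Weeks 26, 34 and 42 as predictors, followed by ANCOVA and Rubin's rules.
2. Pre-specify Copy Reference and tipping-point analyses at Week 52 as sensitivity analyses in their own right, not only as a non-convergence fallback, because pattern-mixture with rescued, on-drug donors may remove only part of the bias.
3. Derive HbA1c <7.5%, <7.0% and <6.5% at Weeks 26 and 52 from the imputed HbA1c values, combine by Rubin's rules, and report the difference in proportions with its interval. This also removes the need for the LOCF fallback.
4. Keep MMRM and the GLMM as sensitivity analyses.

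The cost is mainly reuse of code already specified for the primary endpoint. Expect slightly wider intervals and a limited donor pool. The large-sample runs above do not show how stable the imputation model would be at 73 per arm.
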